7.6 Treatment Discontinuation

7.6.1 Criteria for Treatment Discontinuation

SL-401 treatment may be discontinued for any of the following reasons:

- Patient withdrawal of consent
- Occurrence of unacceptable toxicity, including DLT
- SL-401 related anaphylaxis or Grade \geq 3 hypersensitivity reaction
- Requirement for $>$ 1 dose reduction unless there is evidence of AML/BPDCN response (beyond Cycle 1), in which case additional dose reductions are permitted, however these

reductions must be discussed with the Medical Monitor and documented in the context of ongoing AML/BPDCN response

- Disease recurrence/progression
- Intercurrent illness that prevents further administration of SL-401
- Patient non-compliance
- Occurrence of pregnancy
- Investigator's decision

The reason for SL-401 discontinuation and the date of discontinuation should be recorded in the eCRF.

In settings in which there is preliminary but not conclusive evidence of disease progression (i.e., new skin lesions of indeterminate etiology, new lymph nodes $\leq 1.5\text{cm}$, modest increase in bone marrow blast percentage subsequent to an initial marked reduction, appearance of new blast population on bone marrow evaluation by means of flow cytometry or other molecular methodology without increase in blast percentage consistent with PD), additional SL-401 cycles may be administered, provided that the Investigator documents that the evidence of potential disease progression is inconclusive and that the overall risk/benefit assessment favors additional investigational therapy. Additional SL-401 may also be administered in situations of mixed response BPDCN in which response/progression is not consistent between a given patient's disease sites, provided that the Investigator documents that the overall risk/benefit assessment favors additional investigational therapy. In such situations, it is essential that relevant findings and assessments are documented, and that areas of potential disease progression are followed closely on subsequent assessments.

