7.6.2 Procedures and Follow-up after Treatment Discontinuation

The evaluation during which the Investigator determines that SL-401 will be discontinued should be considered the End of Treatment Evaluation; all tests and procedures for the End of Treatment Evaluation are listed in [Table 6](#) and [Table 8](#) (in [Section 9.8](#)). In addition, patients should be followed for a minimum of 30 days after the last infusion of SL-401 for assessment of AEs (including potential new AEs and potential change/resolution of existing AEs).

If the patient is in CR/PR at the time of discontinuation, disease assessments should continue to be performed as described in [Section 8.12](#) on an every 6-week basis (± 1 week) through 6 months post-C1D1 and then on an every 90-day basis or until, in the judgment of the Investigator, there is evidence of relapsed or progressive disease. Beyond the End of Treatment Evaluation and 30-day follow up (safety/AE assessment), it is requested that subsequent follow-up occur approximately every 90 days for survival status. (If the patient is in CR/PR at the time of discontinuation, disease assessments should continue to be performed as described in [Section 8.12](#) on an every 6-week basis (± 1 week) through 6 months post-C1D1 and then on an every 90-day basis or until, in the judgment of the Investigator, there is evidence of relapsed or

progressive disease. Patients who undergo SCT will be followed for the occurrence of VOD and engraftment delay or failure as part of survival monitoring.

If the patient discontinues SL-401 treatment and also withdraws consent for collection of future information, no further evaluations should be performed and no additional data should be collected as part of the study. The Sponsor will only retain and use any data collected before withdrawal of consent.

Please consult [Section 6.4](#) for recommendations concerning ongoing follow-up of patients alive with or without evidence of disease progression at the time of Study Completion/assessment of primary and critical secondary endpoints.

8 Study Procedures

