- **CT scans** of index lesions 21 (± 7) days after the start of Cycles 2, 4 and 6 and 21 (± 7) days after the start of every 4th cycle thereafter (for patients with baseline evidence of lymph node or visceral disease) until there is evidence of relapsed or progressive disease. For patients with no baseline evidence of lymph node or visceral BPDCN involvement, subsequent scans should be performed at the end of Cycle 2 (± 7 days; or at time of disease progression (PD) if PD occurs prior to end of Cycle 2), 21 (± 7) days after the start of Cycle 6, and at Investigator’s discretion thereafter. Baseline CT scans should be full-body (chest/ abdomen/pelvis), whereas follow-up scans should document response of index lesions ([Cheson et al. 2007](#)).
 - During Stages 2-4, subsequent to the end of Cycle 2, imaging at intervals less frequent than those stipulated above may be permitted when required by local regulations; however, this must be reviewed with the Medical Monitor (or designee).
 - For patients in Stages 2-4, electronic copies of all baseline and subsequent CT scans will be submitted to a central archive (scans are to be submitted regardless of the presence/absence of BPDCN-related abnormalities).
- Collection of **peripheral blood samples** for determination of blasts 21 (± 7) days after the start of Cycles 1 and 2. Patients with evidence of peripheral blasts at baseline will also have peripheral blood samples collected 21 (± 7) days after the start of every 2nd cycle thereafter (Cycles 4, 6, etc.) until there is evidence of relapsed or progressive disease.

Tumor response will be assessed by the Investigators for all patients with BPDCN, with the Investigator's assessment to be used in the primary analysis. As a supportive assessment, tumor response was also evaluated by an IRC on a pre-specified subset of patients. Tumor response will be assessed using the Tumor Response Criteria for Patients with BPDCN presented in [Section 16.2, Appendix B](#). All patients will also be followed for DOR and survival until study completion.

[figure not shown]

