9.6 Safety Monitoring: Through 30 Days after Last Infusion

All Patients, All Study Stages:

- AE and SAE monitoring
- Survival status

9.7 Survival Monitoring: Approximately Every 90 Days after End of Treatment until Study Completion

Patients in PR/CR at End of Treatment:

- Survival status and response/disease progression status, continuing until assessments of the primary and secondary objectives are completed for all patients; survival status may be performed by telephone contact.
- Patients who undergo SCT will be followed for the occurrence of VOD and delayed or failed engraftment as part of survival monitoring.

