- (m) Following treatment with premedication, SL-401 will be administered as a 15-minute infusion for the first 5 consecutive days of a 21-day cycle. Individual SL-401 infusions may be delayed to allow for toxicity resolution; all infusions should be completed within 10 days and fewer than 5 infusions are permitted in settings of incipient CLS or hepatotoxicity. Patient must be monitored for 4 hours post infusion.
- (n) Plasma samples (6 mL each) will be collected immediately prior to the start of the infusion of SL-401, immediately after end of infusion (time recorded), then 15, 30, 45, 60, 90, 120, 180, and 240 minutes after the start of the infusion during infusions 1 (i.e., Day 1) and 5 (i.e., Day 5) of [Cycles 1 & 3](#) (see [Table 9](#)).
- (o) Blood samples (10 mL) will be collected for the detection of SL-401 reactive antibodies on Day 1 (pre-infusion), Day 15, and Day 21 (if patient is to receive additional cycles, can be Day 1, pre-infusion for next cycle). If infusions are held, please collect a sample within 3 \pm 3 days after the last SL-401 infusion of the cycle.
- (p) After the follow-up visit, patients will then be followed every 90 days for survival status. The survival follow-up may be by telephone contact. If the patient is in CR/PR at the time of discontinuation, disease assessments should continue to be performed as described in [Section 8.12](#) on an every 6-week basis (\pm 1 week) through 6 months post-C1D1 and then on an every 90-day basis or until, in the judgment of the Investigator, there is evidence of relapsed or progressive disease. Patients who undergo SCT will be followed for the occurrence of VOD and delayed or failed engraftment as part of survival monitoring.
- (q) For Cycles 5 and beyond (Stages 2-4), the Day 8 and 15 concomitant medication and AE evaluations may be conducted via telephone and the laboratory evaluations may be performed at local laboratories for patients who live a considerable distance from the study center.

Table 9: Time Points for Pharmacokinetic Blood Draws and ECGs

Time Point	Cycle: Day/Dose							
	Cycle 1: Day 1/Infusion 1		Cycle 1: Day 5/Infusion 5		Cycle 3: Day 1/Infusion 1		Cycle 3: Day 5/Infusion 5	
	ECG	PK	ECG	PK	ECG	PK	ECG	PK
Pre-Infusion	X	X	X	X	X	X	X	X
Immediately After End of Infusion (time recorded)		X		X		X		X
15 Minutes Post-Infusion		X		X		X		X
30 Minutes Post-Infusion	X	X	X	X	X	X	X	X
45 Minutes Post-Infusion		X		X		X		X
60 Minutes Post-Infusion	X	X	X	X	X	X	X	X

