4.3.4. Progression-Free Survival

Progression-free survival is defined as the time from the date of first infusion of tagraxofusp to the date of PD or death from any cause, whichever occurred first. For patients who receive SCT, PFS will include time to PD or death post-transplant. Patients who do not progress and are still alive at the time of analysis will be censored on the date of last treatment recorded prior to the analysis cut-off date. If patients start other anticancer therapies (with the exception of SCT), they will be censored at the latter of the date of last treatment with tagraxofusp or date of last disease assessment recorded that occurred prior to the start of the new therapy. The distribution for PFS will be estimated by Kaplan-Meier methodology and the 25th percentile, median, 75th percentile, number and percentage of events and censored observations, and appropriate CIs will be presented.

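### Patients who stop SL-401 outside CR/PR and without progression have no scheduled progression follow-up, so PFS in R/R BPDCN and AML may be overstated

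*Protocol*

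**What the plan says.** - Protocol 7.6.2, after discontinuation: "If the patient is in CR/PR at the time of discontinuation, disease assessments should continue to be performed as described in" Section 8.12, every 6 weeks up to 6 months from the first dose and every 90 days after that. For patients in general, "it is requested that subsequent follow-up occur approximately every 90 days for survival status".
- Footnote (p) of Tables 6 and 8 (Protocol 9.8) repeats this: "After the follow-up visit, patients will then be followed every 90 days for survival status". Telephone contact is allowed, and disease assessment is again tied to CR/PR.
- Protocol 9.7 does collect more at these contacts: "Survival status and response/disease progression status, continuing until assessments of the primary and secondary objectives are completed for all patients". That line stands under a heading restricted to patients in PR or CR at End of Treatment.
- Protocol 9.5 lists performance status, physical examination, vital signs with weight, and vision at End of Treatment. It lists no tumour assessment.
- Protocol 8.12.3 schedules BPDCN assessments "until there is evidence of relapsed or progressive disease", and 8.12.2 does the same for AML in Stage 2. Neither is limited to responders or to time on treatment.
- Protocol 7.6.1 names progression as one of nine reasons for stopping, and adds: "The reason for SL-401 discontinuation and the date of discontinuation should be recorded in the eCRF".
- SAP 4.3.4: "Progression-free survival is defined as the time from the date of first infusion of tagraxofusp to the date of PD or death from any cause", taking the earlier of the two. Patients alive without progression are censored at last treatment. "If patients start other anticancer therapies (with the exception of SCT), they will be censored" at the later of last treatment or last disease assessment before that therapy.
- SAP Table 3-1 plans PFS for first-line BPDCN and for R/R BPDCN (Stages 1, 2 and 4 pooled). It plans TTP for first-line BPDCN only. PFS in AML is a secondary objective (Protocol 4.2).

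**The concern.** PFS needs progression to be looked for in every patient until it happens. Here the search stops with treatment for patients who are not in CR/PR, which is a group with a poor outlook. One of the listed stopping reasons, needing more than one dose reduction without evidence of response, can take non-responders off treatment before progression while responders may continue. If their later progression is not recorded, the PFS event is dated too late or the patient is censored early for reasons related to prognosis. Both errors tend to lengthen the PFS curve.

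The new-therapy rule in SAP 4.3.4 adds to this. It needs a start date, but Protocol 9.5 to 9.7 and Tables 6 and 8 schedule no collection of one. If the date is missed, a later death is counted as an event where the rule calls for censoring.

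**Working it through.** **1. The plan's own figures.** No sample size, event count or power is stated for PFS or TTP. The only design calculation is for the Stage 3 CR rate (10 patients, 60% against 10%). The Clopper-Pearson lower bound is 6.67% for 3/10 and 12.16% for 4/10, so success needs at least 4 responders. Power = P(X ≥ 4 | n = 10, p = 0.60) = 0.945, which agrees with the stated minimum of 90%. It does not bear on this point.

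**2. Who has progression recorded.**

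| Patient | Scheduled progression information |
|---|---|
| On treatment | Yes (8.12) |
| Stops because of progression | Yes, as reason and date in the eCRF (7.6.1) |
| Stops in CR/PR | Yes (7.6.2, 9.7, footnote (p)) |
| Stops outside CR/PR for another reason | None under 7.6.2, 9.5, 9.7 and footnote (p); assessments until progression under 8.12.2 and 8.12.3 |

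Only the last row is a gap, and the sections disagree about it.

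**3. What PFS then records.** Take a hypothetical patient who stops in stable disease at month 1.5, progresses unrecorded at month 3 and dies at month 8. The correct PFS is 3 months.
- Death found at a survival contact: event at month 8.
- Alive at the cut-off instead: censored at month 1.5.
- New non-SCT therapy started and recorded: censored at the later of last treatment or last assessment before it.

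**4. How many could be affected.** Protocol 3.7.2 gives an ORR of 69% in 13 R/R BPDCN patients: 9/13 = 69%, leaving 4/13 = 31% non-responders. All 13 were at 12 µg/kg/day, because SAP 3.13.1 has 29 of the 32 interim patients at that dose and 29 − 16 first-line = 13. In first-line patients at that dose the ORR was 100% of 16, leaving 0/16.

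The 4/13 counts all non-responders. Those who stopped without progression are a subset, and their number is not given. As a bound it also assumes that CR/PR in 7.6.2 includes CRi and CRc, since ORR counts both (SAP 4.3.1). SAP 3.1 adds five R/R patients in Stage 4 whose responses are not given.

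**5. Illustration for R/R BPDCN.** This is a Kaplan-Meier simulation of 200,000 patients. Every input except 9/13 is an assumption:
- non-responders' last treatment at 0.7 to 2.1 months;
- 25%, 50% or 75% of non-responders stop without progression;
- median 1.5 months from stopping to progression and 3 months from progression to death;
- 0% or 50% of non-responders start new therapy;
- 30% of responders have long-term control, and the others progress at 1 month plus a median of 6;
- responders' last treatment at 2 to 6 months, or at progression if earlier;
- cut-off at 24 months.

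Median PFS in months; each range covers 0% and 50% new therapy:

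| Stop without progression | All progression seen | Planned, censored at later of last treatment or assessment | Planned, censored at last treatment (SAP 4.3.4 as written) |
|---|---|---|---|
| 25% | 5.69–5.71 | 6.60–6.71 | 5.64–5.65 |
| 50% | 5.93–5.98 | 7.53–7.89 | 6.23–6.32 |
| 75% | 6.15–6.16 | 8.28–8.85 | 6.73–6.85 |

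Under later-of censoring the shift runs from 6.60 − 5.71 = +0.9 to 8.85 − 6.15 = +2.7 months. Under the wording of 4.3.4 it runs from 5.64 − 5.71 = −0.1 to 6.85 − 6.15 = +0.7, because censoring at last treatment discards progression-free time in responders and pulls the other way.

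No range is given for AML. The only AML response count in the documents comes from the earlier Study 50047.

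**The case against.** Much of the progression is captured. Progression on treatment or as the reason for stopping is recorded, deaths are PFS events, and non-responders without clinically significant progression may stay on treatment if they benefit (Protocol 7.5.2). The month-based marrow examinations in 8.12 could find progression in patients with baseline marrow disease, and the End of Treatment visit may coincide with an end-of-cycle assessment. SAP 4.4.6 lists subsequent treatments, so some start dates probably exist. The secondary endpoints are descriptive. All of this stands, and it confines the problem to the last row of the first table. It does not close that row: marrow examinations cover one disease site, and sites must choose between two sets of instructions.

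Four stronger inferences are tempting and are not supported:
- That progression goes uncollected in non-responders generally. It is missing from the schedule only for those who stop for another reason.
- That TTP is biased in R/R BPDCN and AML. TTP is planned only in first-line BPDCN, where the effect is likely small.
- That non-responder shares measure the effect. The 31% is an upper bound. The corresponding 52/59 = 88% in R/R AML (2 CR and 5 PR among 59) comes from a single-cycle study with two regimens and several doses, and does not carry over.
- That PFS is overstated as a matter of fact. Upward is the likely direction, but censoring at last treatment partly offsets it.

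Timing also limits the gain. AML enrolment closed under Amendment 9, Stage 4 enrolment ended in January 2019, and the SAP cut-off is 13 March 2020. New questions recover little for patients already out of follow-up; a count of those affected can still be reported.

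**Conclusion.** The gap is real and narrow. Patients outside CR/PR who stop SL-401 for a reason other than progression have no scheduled progression follow-up under 7.6.2, 9.5, 9.7 and footnote (p), and this conflicts with 8.12.2 and 8.12.3. PFS in R/R BPDCN and AML may be overstated as a result. The documents do not allow the amount to be estimated, because they give neither the share who stop this way nor their time to progression. The simulated shifts of −0.1 to +2.7 months in R/R BPDCN show only how far the answer depends on those unknowns and on the censoring rule. The Stage 3 primary endpoint does not depend on any of this. It is a low-cost improvement to secondary endpoints and does not challenge the main result.

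**What to change.** - In Protocol 7.6.2, 9.7 and footnote (p) of Tables 6 and 8: at each existing 90-day contact, telephone included, record for every patient without prior progression the date and basis of any investigator-documented progression, and the start date of any new anticancer therapy or SCT.
- Reconcile 7.6.2 with 8.12, and state whether CR/PR there includes CRi and CRc.
- In the SAP, report how many patients left treatment without progression or response and had no later disease information.

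The cost is two extra questions at a contact already scheduled, with no added scans or marrow examinations. The drawback is that some progression dates will be clinical and will not meet the full response criteria.

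Dating progression at discontinuation when progression was the stated reason is not a remedy, since the affected patients stopped for other reasons.

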8.1 Patient Selection

Patients with BPDCN or R/R AML who have previously received at least one line of therapy for their disease, previously untreated AML that is considered high risk for disease progression, and who otherwise meet the inclusion/exclusion criteria will be recruited for enrollment into the study. Patients will be advised of the clinical protocol by the Investigator. If the patient is interested and is potentially eligible for participation in the study, he/she will be provided with the ICF to review and sign. The ICF includes a detailed explanation of the study design and the potential risks and benefits of treatment. Patients who agree to participate in the study will be provided with a copy of the signed consent form; the original signed consent document will be filed in the patient's medical record. Only eligible and consenting patients will be entered into the study.

Patients will be screened by the site's Investigator or study nurse/coordinate prior to study entry. All patients enrolled on the study will be entered into a patient registration log at each site. Each screened patient will be assigned a sequential patient/study screening number with digits indicating site number and patient study number (e.g., XX-YYY, where XX denotes site number and YYY denotes patient study number as assigned at screening). Original screening records and source documents should be kept for all patients, including those who fail to meet the patient eligibility requirements and any completed eCRFs should be retained for monitoring and auditing. Each patient's data obtained from subsequent evaluations should be recorded and evaluated in the source documents and eCRF. Prior to treatment, the Investigator will re-confirm patient eligibility criteria and assignment of the correct patient study number.

8.2 Medical History

Medical history includes current and past medical conditions and smoking history, date of AML or BPDCN diagnosis, prior AML/BPDCN treatment, response to prior treatment, and date of relapse, if applicable. Information concerning any prior malignant diagnoses with particular focus on cytotoxic therapies received for prior malignancies (i.e., dates/duration of anthracycline for prior breast cancer) is to be collected whenever feasible.

8.3 Disease Confirmation (Patients with BPDCN in Stages 2-4)

For patients with BPDCN enrolled in Stages 2-4, the BPDCN diagnosis will be made or confirmed during Screening by the pathology laboratories at the investigative sites. Subsequent to enrollment, pathology material will be submitted for review by the central pathologist for confirmation of the BPDCN diagnosis.

Pathology material will consist of pathology slides (or tissue blocks) and associated pathology reports for all organ sites evaluated for BPDCN via histopathology/ cytopathology. In situations in which submission of slides or blood smears is considered not feasible, submission of representative electronic images of histopathology will be permitted. Pathology submission will also include reports of all immunohistochemistry evaluations for BPDCN and other hematologic-malignancy-associated markers, and reports of flow cytometry performed on bone marrow aspirate (or blood if applicable) for BPDCN and other hematologic-malignancy-associated markers. Submission of scatter-plots of flow cytometric evaluation is strongly encouraged.

8.4 Prior and Concomitant Medication

Medications taken within 28 days prior to screening and throughout the study are to be collected and recorded.

8.5 ECOG Performance Status

See [Section 16.4](#) for a scoring guide.

8.6 Physical Examination

Physical examination includes evaluation by body system and height (at screening only).

